6.7 Treatment Accountability and Disposal

The study site personnel is responsible for the accountability of pomalidomide and dexamethasone. The investigator will dispense the proper number of each strength tablet to the subject to satisfy dosing requirements until the subject's next visit. The subject must be instructed to return all unused study medications in the provided packaging at each subsequent visit. The investigator is responsible for the inventory of each batch of IP received and for accounting for all IP that is issued to and returned by the subjects during the study. Any remaining IP after the completion of the study, will be counted, documented and destroyed according to standard operating procedure.

7. EFFICACY ASSESSMENTS

7.1 Efficacy assessment

It must be conducted at the same time points for all subjects during their participation in the study in order to accurately compare PFS between the two treatment arms. These assessments include: myeloma paraprotein protein electrophoresis and immunofixation, serum immunoglobulins, serum free light chain assay, serum hematology (hemoglobin), serum chemistry (corrected serum calcium and creatinine) and bone marrow aspirate. They must be performed at the start of each cycle (28 days). Treatment response must be assessed using results from the central study laboratory.

7.2 Response assessment

Starting from the second Cycle, response will be evaluated by the investigators according to the EBMT criteria, using results from central site laboratories, at every Day 1 of every cycle until PD (PFS phase). All treatment discontinuation decisions will be made by treating physicians based on the central laboratory results. In the Long-term follow-up phase (OS phase) subjects will be contacted every 2 months for 2 years after the randomization of the last subject. Survival time, cause of death and any subsequent anti-MM treatments should be recorded on CRFs.

7.3 Definitions of Response Based on EBMT Criteria

Complete Response (CR)/stringent CR (sCR)

A CR requires that all of the following criteria be achieved:

1. Negative immunofixation (“IF”) on both serum and urine, maintained for a minimum of 6 weeks and
2. A bone marrow aspirate or biopsy containing < 5% plasma cells. It is not essential to perform a trephine biopsy, but if a biopsy is performed this must also contain <5% plasma cells (although not required for documentation of CR using the EBMT criteria, light chain restriction (flow or IHC for kappa and lambda light chain in the bone marrow should also be assessed to assist in classification of stringent CR using the IMWG criteria)¹⁷ and
3. If skeletal survey showed osteolytic bone lesions, there should be no increase in the size or number (development of a compression fracture does not exclude response) and
4. If screening scans showed extramedullary plasmacytomas, complete disappearance of any must be noted.

For assessment of stringent CR, per IMWG criteria, all criteria for CR must be upheld. In addition, bone marrow sample must be assessed for light chain restriction (as mentioned in bullet 2 above) and serum free light chains must be normalized at two time points at least 6 weeks apart, at the time of CR assessment.

Partial Response (PR)

Subjects in whom some, but not all, the criteria for CR are fulfilled are classified as PR, providing the remaining criteria satisfy the requirements for PR. This includes subjects in whom routine electrophoresis is negative but in whom IF has not been performed.

1. Greater than or equal to 50% reduction in serum M-protein, maintained for a minimum of 6 weeks.
2. Reduction of 90% in urinary light chain excretion or a decrease to < 200 mg/ 24 hours, maintained for a minimum of 6 weeks.
3. Greater than or equal to 50% reduction in the size of extramedullary plasmacytomas present at baseline (by radiography or clinical examination using bidimensional measurements).
4. If a skeletal survey is performed, no increase in the size or number of lytic lesions (development of a compression fracture does not exclude response).

Very Good Partial Response (VGPR)

VGPR, a subset of PR, is not formally included in the EBMT criteria but is derived from the IMWG criteria.

Because VGPR is commonly used to measure depth of response in MM, this response must be reported by investigator and IRC and is defined by:

1. Serum and Urine M-protein detectable by immunofixation but not on electrophoresis and that is confirmed in a subsequent assessment OR
2. 90% or greater reduction in serum M-protein plus urine M-protein level < 100 mg per 24 h and that is confirmed in a subsequent assessment.

Minor (Minimal or Marginal) Response (MR)

Subjects who have reduction in M-protein or plasmacytoma but do not meet the criteria for PR are classified as MR if they meet all the following definition:

1. Between 25 - 49% reduction in serum M-protein, maintained for a minimum of 6 weeks.
2. Between 50 - 89% reduction in urinary light chain excretion which still exceeds 200 mg/24 hours, maintained for a minimum of 6 weeks.
3. Between 25 - 49% reduction in the size of extramedullary plasmacytomas.
4. If a skeletal survey is performed, no increase in the size or number of lytic lesions (development of a compression fracture does not exclude response).

Progression of Disease (PD)

Progression: Progression describes a definite increase in disease activity relative to the nadir in 2 consecutive assessments in subjects not in CR, whereas the term "relapse from CR" applies to a recurrence of evident disease in subjects previously in CR. The date of EBMT based disease progression is the first date of two consecutive values fulfilling the criteria for disease progression. Any of the following list is sufficient for PD:

1. Increase of > 25% in serum M-protein (also an absolute increase of at least 5 g/L) and confirmed by at least 1 investigation.
2. Increase of > 25% urinary light chain excretion (which must also be an absolute increase of at least 200 mg/24-hours and confirmed by at least 1 investigation).
3. Increase of > 25% plasma cell percentage in the marrow (which must also be an absolute increase of at least 10%).
4. Definite increase in the size or number of lytic bone lesions or extramedullary plasmacytomas (development of a compression fracture does not exclude continued response and may not indicate progression).

5. Development of hypercalcemia (corrected serum calcium greater than 11.5 mg/dL; 2.8 mmol/L) not attributable to any other cause.

Relapse from CR (for subjects in CR): Subjects who have documented CR and then achieve at least one of the following criteria are classified as relapse from CR. According to the EBMT criteria, relapse from CR is considered to be progression of disease. The date of EBMT based relapse from CR is the first date of two consecutive values fulfilling the criteria for relapse.

1. Reappearance of serum or urinary M-protein on immunofixation or routine electrophoresis, confirmed by at least one further investigation and excluding oligoclonal reconstitution.
2. Greater than or equal to 5% plasma cells in a bone marrow aspirate or on trephine bone biopsy.
3. Any of the definitions met for Progression

Stable Disease/No Change

Does not meet criteria for any of the categories above.

8. MANAGEMENT OF ADVERSE EVENTS

8.1 Adverse events definitions

A treatment-emergent AE is any untoward medical occurrence in a study subject administered an investigational product and that does not necessarily have a causal relationship with this treatment. An unexpected AE is any adverse drug event, the specificity or severity of which is not consistent with the current Investigator's Brochure or prescribing information for a marketed compound. Also, reports which add significant information on specificity or severity of a known, already documented AE constitute unexpected AEs. For example, an event more specific or more severe than described in the Investigator's Brochure would be considered "unexpected". An AE, therefore, can be any unfavorable and unintended sign (including clinically significant laboratory finding, as determined by the investigator), symptom, or disease temporally associated with participation in an investigational study, whether or not considered treatment-related. In addition to new events, any increase in the severity or frequency of a preexisting condition that occurs after the subject signs a consent form for participation is considered an AE. This includes any side effect, injury, toxicity, or sensitivity reaction.

8.2 Severity description

GRADE 1 – Mild Transient or mild discomfort; no limitation in activity; no medical intervention/therapy required.

GRADE 2 – Moderate Mild to moderate limitation in activity—some assistance may be needed; no or minimal medical intervention/therapy required.

GRADE 3 – Severe Marked limitation in activity, some assistance usually required; medical intervention/therapy required, hospitalizations possible.

GRADE 4 – Life-threatening Extreme limitation in activity, significant assistance required; life-threatening (immediate risk of death); significant medical intervention/therapy required, hospitalization or hospice care probable.

GRADE 5 – Fatal Death

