Bortezomib (Velcade®) is an anti-neoplastic agent which was approved by the FDA in 2003 (3rd line) and 2005 (2nd line) for relapsed/refractory patients with MM. Response rates of around 30% in relapsed patients have been reported with <3% CR (5). However, AEs occurring in 30-70% of patients include anorexia, constipation,

thrombocytopenia, neutropenia, pyrexia, vomiting, and anemia. Of particular importance, treatment-associated peripheral neuropathy is frequently reported. Recently, bortezomib has been tested in 1st line setting as induction therapy with an ORR of 49%, with no CR (n=43, phase II) (6) and in 2nd and 3rd line settings with an ORR of 70% and CR of 3-12% (Phase III studies of n=624, n=104, and n=333) (7;8), (9). Furthermore, clinical trials with bortezomib in combination with other therapies, including dexamethasone, dexamethasone/doxorubicin, revlimid, and melphalan/prednisone have been conducted. Especially, bortezomib in combination with melphalan/prednisone as 1st line has yielded high response rates of 89% including CR of 32% and a 2-year survival of 86% (n=60, phase I/II) (10). However, high frequencies of side-effects were observed, including thrombocytopenia (51% of the patients), neutropenia (43%) and neuropathy (17%). Recently, combination of bortezomib with thalidomide as 1st line therapy has also yielded high response rates (82%) (n=30), however all patients developed neurological AEs (11). Also, bortezomib in combination with dexamethasone, 1st line, is shown to yield high response rates of 90% with CR/near CR of 19% (n=48, phase II) (12). Additionally, a quadruple combination with bortezomib, MP and thalidomide in 2nd/3rd line has shown high response rates (70-80%) with CR in around 30% of the patients (n=30, phase I/II) (13). However, the high frequency of associated SAEs of grade 3 and 4 such as thrombocytopenia (~30%), neutropenia (~40%) and peripheral neuropathy (~5%) should be noted. In summary, bortezomib is currently used as 2nd and 3rd line therapy for relapsed/refractory patients with MM. Future bortezomib combination regimens are likely to include MP or dexamethasone for 1st line therapy.

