Lenalidomide (Revlimid®) is approved 1st line treatment in combination with dexamethasone. As monotherapy in refractory patients, a response rate of 37% with 10% CR has been reported (20). Severe side effects include thrombocytopenia and neutropenia. Lenalidomide plus dexamethasone versus dexamethasone alone in relapsed patients show increased overall response (59% vs. 23%) with CR of 8-17% vs. less than 3%, and increased overall survival (n=346 in each arm, two phase III studies) (21), (22). In addition this combination has also been tested as 1st line treatment showing an ORR of 91% including 18% CR and a 2-year overall survival of 91% (n=34, Phase II) (23), (24). Lenalidomide is also tested in a 1st line setting as an add-on to MP (MPR) vs. MP alone with a reported RR of 85% including a CR of 23% (n=34, Phase I/II) (25). Interestingly, peripheral neuropathy does not seem to be an issue with lenalidomide – in contrast to thalidomide.

Pomalidomide (Investigational Product) is approved for the treatment of MM in patients who have received at least two prior therapies (including lenalidomide and velcade) and have demonstrated disease progression after the last treatment. Pomalidomide is a novel immunomodulatory drug, which shares some of the beneficial pharmacologic properties of lenalidomide and thalidomide. It has shown a 10-fold higher potency for T-cell stimulation than lenalidomide (30) and is more potent than both lenalidomide and thalidomide in inducing G1 growth arrest and apoptosis in MM cell lines and in patients MM cells that are resistant to melphalan, doxorubicin and dexamethasone, as well as enhancing the antimyelomatous activity of dexamethasone (31). Moreover, pomalidomide does not inhibit the proliferation of normal B cells but rather protects them from apoptosis, assisting the repopulation of normal blood cells (32).

Transplantation

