6.6 Dose modifications

Dosing interruption and titration is permitted during the study, Subjects will be evaluated for AEs at each visit. The severity of AEs will be measured. Thus, the dose can be modified if a subject experiences a dose-limiting toxicity (DLT).

Pomalidomide dosing can be reduced to 1 mg starting from 4 mg, in 1 mg increments.

If an AE is resolved in 28 days, then pomalidomide can be re-initiated at full dose. If not, then the dose should be decreased by one increment.

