8.4 Adverse events reporting procedures

All AEs (eg, any new event or worsening in severity or frequency of a preexisting condition or laboratory finding) for randomized subjects with an onset date after the subject signs consent for study participation must be promptly documented on the AE CRF. Details of the event must include severity, relationship to study drug, duration, action taken, and outcome. Non-serious AEs will not be recorded for subjects who screen fail. All SAEs will be recorded from the time of informed consent in the CRF for all subjects.

All AEs for randomized subjects will be collected from the time the subject signs informed consent through PD. In addition, the Investigator should report any AE that may occur after this time period that is believed to have a reasonable possibility of being associated with study drug. All AEs that are considered related to study drug must be followed to resolution or stabilization if improvement is not expected.

Adverse events which completely resolve and then recur should be recorded as a new AE. For the OS phase, a follow up of ongoing AEs should be attempted by telephone, and documented in the subject's source file. The Principal Investigator is responsible for evaluating all AEs, obtaining supporting documents, and determining that documentation of the event is adequate. Laboratory abnormalities should be recorded as AEs on the CRF only if they require treatment or are otherwise considered clinically significant by the Investigator.

All deaths during PFS phase are to be reported as SAEs.

The corresponding entry for progression-related deaths on the AE CRF should use the verbatim term “Disease Progression” rather than the specific sign or symptom that may have been the immediate cause of death. Additional details of the event (such as the primary and contributory causes of death) should be reported on the Death CRF.

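### The only adverse event severity scale has no laboratory criteria, so a very low but symptom-free blood count can be Grade 1, be graded inconsistently, or go unrecorded

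*Protocol*

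**What the plan says.** Protocol section 8.2 is the only severity scale in the document.

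- Grade 1: "Transient or mild discomfort; no limitation in activity; no medical intervention/therapy required".
- Grade 2: mild to moderate activity limitation, with "no or minimal medical intervention/therapy required".
- Grade 3: "Marked limitation in activity, some assistance usually required; medical intervention/therapy required, hospitalizations possible".
- Grade 4: "Extreme limitation in activity, significant assistance required; life-threatening (immediate risk of death); significant medical intervention/therapy required, hospitalization or hospice care probable".
- Grade 5 is death.

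No event-specific toxicity criteria are cited anywhere.

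Section 8.4 makes severity a required detail of each adverse event. For laboratory findings it adds: "Laboratory abnormalities should be recorded as AEs on the CRF only if they require treatment or are otherwise considered clinically significant by the Investigator".

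Section 6.6 refers back to severity: "The severity of AEs will be measured. Thus, the dose can be modified if a subject experiences a dose-limiting toxicity (DLT". Dose-limiting toxicity appears in the abbreviation list but is not defined.

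On which toxicities to expect, the lenalidomide paragraph of section 2.2 says "Severe side effects include thrombocytopenia and neutropenia". Section 6.2 places pomalidomide in the same class as thalidomide and lenalidomide.

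**The concern.** A functional scale suits events that the patient feels. A cytopenia is defined by a count and may be severe before it limits activity. When the scale contains no counts, the grade reflects how the patient feels and what the physician chose to do, not the depth of the abnormality.

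What is at stake is the quality of the safety data. The data monitoring committee is charged with monitoring safety throughout (section 10.7), and the grades are part of what the trial will have to show it. The treatment is open label (section 4.5), so the judgements on clinical significance and on intervention are made with the arm known.

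This is not a detail that can wait for the statistical analysis plan. The protocol itself fixes both the scale and the recording rule, and a grade that was not collected cannot reliably be restored at analysis.

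**Working it through.** No arithmetic applies to the defect itself. The check is to take one event, a very low neutrophil or platelet count, and pass it through sections 8.4 and 8.2 as written.

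| Situation | Recorded under 8.4? | Grade under 8.2 |
|---|---|---|
| No symptoms, not treated, judged clinically significant | Yes | Fits Grade 1 on activity and intervention, whatever the count |
| No symptoms, not treated, not judged clinically significant | No | None |
| Treated, no activity limitation | Yes | Indeterminate (see below) |
| Activity limited and treated | Yes | The scale can be applied, but it grades the limitation and not the count |

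The third row works out as follows.

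1. Grade 1 is excluded because it requires that no intervention be needed.
2. Grade 2 allows minimal intervention but expects some activity limitation.
3. Grade 3 fits on intervention but not on marked activity limitation.
4. Grade 4 pairs significant intervention and immediate risk of death with extreme activity limitation. The scale gives no count at which an investigator should consider it.
5. The section does not say whether all descriptors of a grade must be met or any one is enough. Two sites could grade the same count differently.

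Two further comparisons bear on whether something else in the protocol fills the gap.

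- **Worsening from baseline.** Section 8.1 counts an increase in severity of a pre-existing condition as an adverse event. Section 5.2 admits subjects with platelets of 50 × 10^9/L and neutrophils of 1.0 × 10^9/L. Without laboratory grades, no common standard shows when such a baseline cytopenia has become more severe.
- **Regrading later from laboratory data.** The per-cycle list in section 7.1 is an efficacy list, and the only haematology parameter that it names is hemoglobin. The protocol text gives no on-treatment schedule for neutrophil or platelet counts, so later regrading is not assured.

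**The case against.** The strongest reply has four parts.

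1. **There are partial safeguards.** Section 8.1 treats clinically significant laboratory findings as adverse events, and section 8.4 requires them to be recorded whether or not treated. A treated cytopenia must be recorded and is no longer Grade 1. Section 8.5 allows an important medical event to be called serious whatever its grade. This stands and narrows the gap. It does not supply a grade, and each untreated case still rests on an investigator's judgement.
2. **The clinical-significance filter is a deliberate and common choice.** That is so. Combined with a scale that has no laboratory criteria, however, it leaves no objective point at which a count must enter the adverse event record.
3. **No planned analysis is damaged.** The endpoints are PFS and OS, and section 9 plans no comparison of severe adverse events. This stands. The effect is on safety monitoring and reporting, not on the efficacy conclusions.
4. **Section 6.6 is triggered by a dose-limiting toxicity, not by a grade number.** This also stands. The missing definition is a separate weakness. The link here is only that 6.6 invokes measured severity, and 8.2 is the only measure given.

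A reader might also infer more than the document supports:

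- *That cytopenia is the main toxicity the protocol names for the study regimen.* It names none for pomalidomide. The severe effects quoted above are lenalidomide's. The grade 3 and 4 rates in section 2.2 (about 30% thrombocytopenia, about 40% neutropenia) belong to a combination of bortezomib, melphalan/prednisone and thalidomide.
- *That the scale makes Pom/dex look safer than it is.* Both arms use the same scale, and no cytopenia rate is given for either. The direction of any bias is therefore not derivable.
- *That the data monitoring committee would miss a signal.* Section 10.7 does not limit the committee to 8.2 grades.
- *That a number of misgraded subjects can be stated.* Assume that 20% to 40% of the 125 Pom/dex subjects have a marked cytopenia: 0.20 × 125 = 25 and 0.40 × 125 = 50. The share that is symptom-free and untreated is unknown. Letting it run from 0 to 100% gives anything from 0 to 50, which is not an estimate.

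**Conclusion.** The concern holds in a limited form. Section 8.2 has no laboratory criteria and nothing else in the protocol supplies them. A profound, symptom-free, untreated cytopenia can be Grade 1 or can go unrecorded, and a treated one without activity limitation has no determinate grade. Severity grades for laboratory toxicities may therefore be low or inconsistent across the 20 sites.

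Relevance to this trial rests on one inference: that a toxicity described as severe for lenalidomide is foreseeable for a drug that section 6.2 puts in the same class. The number of subjects affected and the direction and size of any difference between arms are unknown. The primary and secondary efficacy analyses are not touched. The change is worth making because it is cheap and because lost grades are hard to recover.

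**What to change.** - **Section 8.2:** name a specific NCI CTCAE version for grading all adverse events, including laboratory values. Keep the present functional descriptors only for events with no CTCAE term.
- **Section 8.4:** record any laboratory value that reaches CTCAE grade 3 or higher as an adverse event, whether or not it is treated. The clinical-significance rule can remain for lower grades.
- **Section 6.6:** reconcile its references to measured severity and to an undefined dose-limiting toxicity with sections 8.2 and 8.4, so that severity has one meaning throughout. No dose rule is proposed here.

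The cost is a wording amendment and a change to CRF coding. The downside is more laboratory adverse events to enter and a higher reported rate of severe events.
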